- Number of AEs, serious adverse events (SAEs), adverse drug reactions (ADRs), and AEs leading to treatment discontinuation during the trial.

Secondary Endpoints:

- Alveolar-arterial oxygen difference ((A-a)DO₂) during the trial.
- 6-minute walking distance (6MWD) during the trial.

- St Georges Respiratory Questionnaire (SGRQ) total score during the trial.
- Frequency of WLL during the trial.
- Diffusion Capacity of the Lung for Carbon Monoxide (DLCO), Forced Expiratory Volume in one second (FEV₁), and Forced Vital Capacity (FVC) during the trial, all expressed as percent predicted.
- Arterial oxygen tension (PaO₂) and disease severity scores (DSS) during the trial.
- Need for oxygen supplement therapy during the trial.
- Number of subjects not requiring treatment for aPAP and time off treatment after discontinuation of inhaled molgramostim

Exploratory Endpoints:

- GM-CSF levels before and 2 hours after dosing

Methods of Assessment:

Lung function variables – DLCO and spirometry (FEV₁ and FVC) will be done in accordance with European Respiratory Society/American Thoracic Society (ERS/ATS) guidance using local equipment. For spirometry percent of predicted values will be calculated centrally using standard equations.

6-minute walking test (6MWT) – will be performed in accordance with European Respiratory Society/American Thoracic Society (ERS/ATS) guidance. Borg CR10 scale will be used to assess dyspnoea before and after the test.

Quality of Life score – SGRQ

Laboratory analyses – Local laboratories will be used for analysis of haematology, clinical chemistry and pregnancy testing.

(For Italy only: samples will be collected for pharmacokinetic (PK) analysis at Visit 1-6, pre-dose and 2 hours post dosing)

Statistical methods:

Data from the trial will be analysed descriptively. Data from the trial is planned to be combined with relevant data from the IMPALA trial; these combined analyses will be reported separately.

Table 1: Study Flow Chart

Visit	Visit 1	Visit 2	Visit 3	Visit 4	Visit 5	Visit 6	Visit 7	FU TC	Unscheduled
	Baseline ^a	Month 6	Month 12	Month 18	Month 24	Month 30	Month 36	2 wks after trial completion	
Time	0	Week 26	Week 52	Week 78	Week 104	Week 130	Week 156		
Visit Window	N/A	± 4wks	± 4 wks	± 4 wks	± 4 wks	± 4 wks	± 4 wks	+ 1 wk	
Informed consent	X								
Eligibility criteria	X								
Demographics	X								
Concomitant medication	X	X	X	X	X	X	X		X
WLL information ^b	X	X	X	X	X	X	X		X

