5.3. Study Endpoints

5.3.1. Primary Endpoints

Number of AEs, SAEs, adverse drug reactions (ADRs), and AEs leading to treatment discontinuation.

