6. INVESTIGATIONAL PLAN

6.1. Overall Study Design

Subjects with aPAP who have completed the IMPALA (MOL-PAP-002) trial will be eligible for this trial.

At the Baseline visit, eligible subjects may continue or re-start treatment with inhaled molgramostim (300 µg) administered intermittently in cycles of seven days molgramostim, administered once daily, and seven days off treatment.

Trial visits will be conducted at 6-monthly intervals until the end of trial. Participating subjects will be encouraged to contact the clinic between visits if they experience AEs or worsening of aPAP, or if they have any other concerns.

During the trial, WLL will be applied as rescue therapy. The criterion for performing WLL is clinical worsening of aPAP based on symptoms, reduced exercise capacity and/or findings of hypoxemia or desaturation according to the investigator's judgement. The reason(s) for conducting WLL will be documented. Subjects undergoing WLL will continue treatment with molgramostim, unless discontinuation is medically required, according to investigator's discretion.

Subjects may discontinue molgramostim due to remission of aPAP, lack of response that requires a different treatment modality, or AEs. Subjects becoming pregnant will be required to discontinue treatment with molgramostim. Subjects who discontinue molgramostim will continue in the trial and attend visits according to the same schedule until end of the trial. Molgramostim treatment may be re-started if medically required. Subjects not requiring treatment at the Baseline visit may start molgramostim treatment during the trial if medically required.

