10.9.2. Recording Adverse Events

All trial subjects will be carefully monitored for the occurrence of AEs during the trial period from Baseline to the last visit. The investigator will collect AEs using a non-leading question such as “have you experienced any new health problems or worsening of existing conditions” as well as reporting events directly observed or spontaneously volunteered by subjects.

Clearly related signs, symptoms and abnormal diagnostic procedure results should be grouped together and reported as a single diagnosis or syndrome whenever possible.

All AEs including but not limited to events reported by the subject, or reported in answer to an open question by the investigator or member of this team, which fall into any of the above definitions must be recorded as an AE in the eCRF and should include the following information:

- Brief description of the event (diagnosis)
- Start date (and time, if relevant)
- Stop date (and time, if relevant) (or resolution)
- Severity
- Action taken regarding trial drug
- Opinion on causality
- Seriousness
- Outcome.

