10.9.3. Reporting Adverse Events

10.9.3.1. Serious Adverse Event (SAE) Reporting Procedure

The investigator is responsible for ensuring that all SAEs are reported to the sponsor immediately, using a trial-specific SAE form, but in any event no later than 24 hours of any site staff becoming aware of the event from the time the informed consent has been signed, up to Day 30 after the last visit. Reporting of SAEs will also be described in a trial-specific procedure.

After that period of time only serious adverse reactions (events related to trial medication) have to be reported. SAEs occurring to a patient after the patient has completed the clinical trial and for which a reasonable possibility of a causal relationship is assessed by the Investigator, must be reported by the Investigator to Premier Research regardless of the time that has elapsed (post-trial events). The SAE form has to be completed in English.

Initial reports should be followed as soon as possible by detailed written reports. The initial and follow-up reports should identify subjects by unique code numbers assigned in the trial. The subjects' names, personal identification numbers, and/or addresses must not be included. The following information is **mandatory** for the initial report:

- Subject trial ID
- Trial treatment (blinded, if applicable)
- Start date (time, if relevant) of the trial treatment
- Brief description of the event (diagnosis)
- Start date (time, if relevant) of the event
- Seriousness criteria
- Causality assessment.

For reported deaths, the investigator should supply the sponsor and the IEC/IRB (if applicable) with any additional requested information (e.g. autopsy reports and terminal medical reports).

The Investigator must contact Premier Research by email or fax directly to Premier Research Pharmacovigilance and Device Safety in case of all SAEs **within 24 hours after awareness of the event**.

SAE REPORTING CONTACT DETAILS

Company: Premier Research

Department: Pharmacovigilance and Device Safety (PVDS)

E-mail: [contact]

[contact]

Note: If there is local legislation requiring investigators to report AEs to the Competent Authority or the IEC/IRB, the investigator should also comply with this legislation. If any such reporting is planned, this must be stated in the SAE report, and once the reporting has been performed, a copy of the reporting documentation must be enclosed with the SAE-Follow-Up report to the sponsor.

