11. STATISTICS

No formal sample size calculation was done as this is an open-label extension trial. Up to 90 subjects will be included.

Data will be summarised using summary statistics. Continuous data will be presented with the number of observations, mean value, standard deviation, minimum, quartile 1, median, quartile 3 and maximum value. Categorical data will be presented as counts and percentages. The data will be presented by visit in tables and graphs. Individual subject data will be listed. Further details of all analyses will be given in the statistical analysis plan.

No “analysis sets” (intention to treat, per protocol, etc.) are defined. All subjects will be included in the analyses/data presentations (equivalent to a Full Analysis Set).

Only recorded data will be analysed/presented and any subjects who have missing data will only have observed data reported, with no imputation for missing data.

Interim cuts of data may be done on a yearly basis and as needed for regulatory purposes (e.g. 120-day safety update).

Data listings will show all recorded data.

Data from the trial is planned to be combined with relevant data from the IMPALA trial; these combined analyses will be reported separately.

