8.1.1 Analysis and Presentation of Safety Parameters

8.1.2 Adverse Events

All adverse events (AEs) occurring after informed consent will be reported in the eCRF. AEs will be coded using the Medical Dictionary for Regulatory Activities (MedDRA) version 21.0.

Adverse events are considered treatment emergent if the onset of the events is on or after the first exposure date of IMP in this trial and until (estimated) last drug date + 7 days. Last drug date is defined as last kit date + 21 days or end of trial date whatever comes first. Only treatment emergent events will be included in the safety summaries.

Possible or probable related AE's are defined as ADRs.

Adverse events will be presented as described in section 7.1.

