8.2 Safety Update

A safety update will be performed with a planned data cutoff 1-February 2019.

The output generated for the safety update is listed below. For the output in section 14.2.4 (Whole lung lavage) the date of the cutoff will be used to calculate subject years.

- Table 14.1.1, 14.1.3, 14.1.5, 14.1.6
- Tables 14.2.4.1, 14.2.4.3
- Table 14.2.6.1
- All output in section 14.3
- Listing 16.2.6.4

9 Deviations from Protocol

A safety analysis set has been added. At the time of protocol generation all patients were expected to be treated from the beginning of this trial. Since some patients are not treated in this trial it was decided to include a safety analysis set

The secondary endpoint “time off treatment after discontinuation of inhaled molgramostim” is not reported due to insufficient data collection.

10 Software

All statistical calculations described in this SAP will be done by BioStata Aps using SAS, release 9.4 or later (SAS Institute, Cary, NC, USA).

11 Reference List

St George's respiratory questionnaire manual version 2.3, 2019, Paul Jones

12 List of Listings

- Listing 16.2.1.1 Violations of inclusion and/or exclusion criteria – screening failures
- Listing 16.2.1.2 Individual subject disposition (all subjects)
- Listing 16.2.1.3 Reason for withdrawal from trial (all subjects)
- Listing 16.2.2.1 Protocol deviations (all subjects)
- Listing 16.2.4.1 Individual subject demographics and baseline characteristics (all subjects)
- Listing 16.2.4.2 Individual medical history (all subjects)
- Listing 16.2.4.3 Individual concomitant medication (all subjects)
- Listing 16.2.4.4 COVID-19 positive subjects (all subjects)
- Listing 16.2.4.5 Adverse events occurring in COVID-19 positive subjects (all subjects)
- Listing 16.2.4.6 Protocol deviations due to COVID-19 (all subjects)
- Listing 16.2.5.1 Individual subject exposure (all subjects)
- Listing 16.2.5.2 Individual subject relative exposure (all subjects)
- Listing 16.2.5.3 Individual visits attended (all subjects)
- Listing 16.2.6.1 Individual (A-a)DO₂ (all subjects)
- Listing 16.2.6.2 Individual 6-minute walk test (all subjects)
- Listing 16.2.6.3 Individual St Georges respiratory questionnaire scores (all subjects)
- Listing 16.2.6.4 Individual whole lung lavage (all subjects)
- Listing 16.2.6.5 Individual lung function tests (all subjects)
- Listing 16.2.6.6 Individual disease severity scores (all subjects)
- Listing 16.2.6.7 Subjects with oxygen supplement during trial (all subjects)

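### SAP 8.1.2 limits every adverse event summary to treatment-emergent events in dosed subjects, which narrows the protocol's primary endpoint, and SAP section 9 does not declare the time limit

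*SAP*

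**What the plan says.** **Protocol.** The synopsis gives the primary endpoint as "Number of AEs, serious adverse events (SAEs), adverse drug reactions (ADRs), and AEs leading to treatment discontinuation during the trial". Section 5.3.1 has the same list without the closing words: "Number of AEs, SAEs, adverse drug reactions (ADRs), and AEs leading to treatment discontinuation". Section 11.1 matches 5.3.1. None of the three sets an on-treatment limit.

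Collection does not depend on treatment status. Section 10.9.2 says "All trial subjects will be carefully monitored for the occurrence of AEs during the trial period from Baseline to the last visit", and section 10.9.3.1 requires SAE reports "from the time the informed consent has been signed, up to Day 30 after the last visit". Section 6.1 says "Subjects who discontinue molgramostim will continue in the trial and attend visits according to the same schedule until end of the trial"; section 7.3.1, and SAP 3.2, use the softer word encouraged. Section 11 says of the population: "All subjects will be included in the analyses/data presentations (equivalent to a Full Analysis Set".

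**SAP.** Section 4 defines a safety analysis set of subjects exposed within this trial and uses it for safety summaries. Section 8.1.2 calls an event treatment emergent if its onset lies between the first dose in this trial and the estimated last drug date plus 7 days. The last drug date is the earlier of last kit date plus 21 days and the end of trial date. The section then says: "Only treatment emergent events will be included in the safety summaries". Section 9 explains the added set: "Since some patients are not treated in this trial it was decided to include a safety analysis set". It does not mention the restriction by onset date.

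**The concern.** A treatment-emergent table is ordinary practice. Here, though, it is the only tabulation of the primary endpoint, and it counts something narrower than the protocol describes. Off-drug follow-up is part of this design: stopping, staying and re-starting are all foreseen, and maintenance of effect after discontinuation is a secondary objective.

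The objective is safety of long-term use. A delayed event, or one in a subject who stopped because of an AE or worsening disease, is the kind that falls after the window. The protocol itself expects related events to surface late: sections 10.9.1.2 and 10.9.3.1 ask for related SAEs even after the subject has left the trial. Under the SAP, an event the investigator judges related is missing from the ADR tables if it starts outside the window. A reader of the report would take the tabulated number as the protocol's endpoint, with nothing in the SAP's list of deviations to say otherwise.

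**Working it through.** The trial is descriptive and has no sample size or power figure to reproduce. The check compares definitions and then works out when the window closes.

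**1. Scope, side by side**

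| | Protocol | SAP |
|---|---|---|
| Subjects | All (section 11) | Dosed in this trial (sections 4 and 8) |
| Start | Baseline; consent for SAEs (10.9.2, 10.9.3.1) | First dose in this trial (8.1.2) |
| End | Last visit; Day 30 after it for SAEs | min(last kit date + 21, end of trial) + 7 days |

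**2. Does the rule reach the primary endpoint?** Yes. Section 8.1.2 refers to 7.1 for presentation, and 7.1 is the primary endpoint section. Tables 14.3.1.2 to 14.3.1.23 all carry treatment emergent in their titles. The overview, Table 14.3.1.1, does not, but the sentence in 8.1.2 covers all safety summaries. No table of events outside the window is listed. Listings 16.2.7.1 to 16.2.7.4 are on all subjects.

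**3. When the window closes.** Let K be the last kit date and E the end of trial date, in days from Visit 1. The window ends at W = min(K + 21, E) + 7. Full planned follow-up is 156 × 7 = 1092 days. Suppose a subject stops for good, is followed to Week 156, and has a last kit date on the visit day (both assumptions). Follow-up outside the window is then 1092 − W:

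| Last kit date | K | W | Outside window |
|---|---|---|---|
| Baseline | 0 | 28 | 1064 days (97%) |
| Month 6 | 182 | 210 | 882 days (81%) |
| Month 12 | 364 | 392 | 700 days (64%) |
| Month 18 | 546 | 574 | 518 days (47%) |
| Month 24 | 728 | 756 | 336 days (31%) |
| Month 30 | 910 | 938 | 154 days (14%) |

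These are upper limits for one subject, because the trial closed early. The SAP does not define last kit date. If it means the day a 26-week supply is dispensed, part of this time is still on drug.

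**4. How many subjects.** SAP 3.2 gives 5 of 60 untreated at termination: 5/60 = 8.3%. Those dosed earlier in this trial lose their events after W. Those never dosed are outside the safety set altogether. The split is not stated, so the number previously dosed is 0 to 5. Time off drug is not stated either.

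**5. Before the window.** Subjects untreated at Baseline may start later (protocol 6.1), so their events before the first dose are not tabulated. Nor are the post-IMPALA events that protocol 10.3 asks sites to report as AEs at Visit 1, because their onset precedes dosing in this trial.

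**6. Declaration.** SAP section 2 says deviations from the protocol analysis are highlighted in section 9. Section 9 has two entries: the added safety set, and the time-off-treatment endpoint, which will not be reported. Adding a set tells the reader that undosed subjects are excluded. It does not say that events in dosed subjects are excluded by onset date.

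**The case against.** The strongest reply is that this is detail which protocol section 11 leaves to the SAP. The explicit reference to the whole trial is in the synopsis only, the objective concerns use of the drug, and the AE definition in 10.9.1.1 refers to temporal association with the product. The window allows up to 28 days after the last kit date, and protocol 4.1 gives a systemic half-life of about 4 hours. All of that supports having a treatment-emergent table. It does not support having no other table, since neither 5.3.1 nor 11.1 narrows the endpoint and section 11 includes all subjects.

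The second reply is that nothing is lost, and that stands. A reader might infer that late events go unreported. They do not: the AE, SAE, ADR and discontinuation listings cover all subjects and show analysis-set membership, and with 60 subjects each late SAE can be found by reading. Because ADRs are defined by relatedness alone, a late related event stays in the ADR listing. But a listing gives no count, rate or denominator, and the endpoint is a number of events.

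Three other inferences go too far:

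- **A figure for missing AEs or SAEs.** It would need off-drug durations and event rates, and the documents give neither.
- **That the SAP is inconsistent because lavages are counted over full time in trial.** Lavage frequency is a secondary efficacy endpoint, and a different counting period for it is legitimate. The window does run through off-drug gaps before a re-start, but that counts more events, not fewer.
- **That all primary components suffer equally.** AEs leading to discontinuation normally begin before the drug stops, so that count is largely unaffected.

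**Conclusion.** The point holds. Following the SAP gives primary-endpoint counts that differ in scope from the protocol's, both by onset date and by subject, and the restriction by onset date is not declared where the SAP says deviations will be.

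The effect on the results cannot be sized. It may be small: at most 5 of the 60 subjects were off treatment at termination. If none of them had been dosed earlier in this trial, the untabulated events in this group are all in never-treated subjects. If all five had been, they are all events after the window. In either case those events enter no table. The per-subject percentages show how the definition works and are not estimates of what happened.

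The conclusion rests on applying the 8.1.2 sentence to every AE summary, including the overview, as its wording and the other table titles indicate. No hypothesis test is affected, because none is planned. The change is worth making because the endpoint is primary and the data are already collected.

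**What to change.** 1. Keep Tables 14.3.1.1 to 14.3.1.23 as treatment-emergent tables, and say so in the title of 14.3.1.1.
2. Add one table to section 14.3, on all subjects, giving AEs, SAEs, ADRs and fatal AEs with onset outside the treatment-emergent window, including those in never-treated subjects. Give subject-years off drug as the denominator. Add a line showing that treatment-emergent plus other events equals all AEs during the trial. Events judged possibly or probably related then enter a tabulated ADR count whatever their onset.
3. Declare the treatment-emergent restriction in SAP section 9 as a departure from the protocol's endpoint.

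The cost is one table and a short statement in the SAP, with no new data collection. The downside is a slightly higher total AE count.

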8.1.3 Physical Examination

All subjects will undergo a standard physical examination at the timepoints shown in Table 1.

Complete physical examinations will include at a minimum a review of the subject's general appearance, head, eyes, ears, nose, and throat (HEENT), neck, heart, lungs, abdomen, extremities, skin, and general neurological system.

No output will be generated for physical examination.

8.1.4 Vital Signs

Vital signs (heart rate, temperature, systolic and diastolic blood pressure) will be measured at each visit including an evaluation for each parameter.

Continuous values of vital signs will be summarized by parameter and visit including change from baseline.

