Based on information from similar products, the potential dose-limiting toxicity of molgramostim would be based on pulmonary effects, such as bronchoconstriction, dyspnoea, cough or decreased pulmonary function. Pulmonary function and respiratory symptoms will be monitored during the trial and treatment should be discontinued if significant worsening occurs. If there is significant systemic exposure, haematologic findings such as leukocytosis and neutrophilia may occur. As non-clinical data indicate that systemic exposure to rhGM-CSF may be associated with increased pre- and post-implantation losses, pregnancy testing will be performed in women of childbearing potential at each trial visit where molgramostim is dispensed and at home at monthly intervals during treatment.

Treatment with molgramostim nebuliser solution is expected to be more effective, less invasive, and more convenient, than the currently available symptomatic treatment, WLL, for patients with aPAP.

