10.8.3. Vital Signs

The following vital signs will be assessed at the timepoints shown in [Table 1](#)

- Resting systolic and diastolic blood pressure (mmHg), after 5 minutes sitting
- Resting heart rate (beats per minute), after 5 minutes sitting
- Resting respiration rate (breaths per minute), after 5 minutes sitting
- Oral body temperature (°C)

The observed values will be recorded and assessed as ‘normal’ or ‘abnormal’. Abnormal findings will be assessed as ‘clinically significant’ or ‘not clinically significant’.

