FAS	Full Analysis Set
GGT	Gamma Glutamyl Transpeptidase
HEENT	head, eyes, ears, nose, and throat
LLOQ	Lower Level of Quantification
MCH	Mean cell haemoglobin
MCV	Mean cell volume
MedDRA	Medical Dictionary for Regulatory Activities
N	Number of Subjects
PT	Preferred Term
SAE	Serious Adverse Event
SAP	Statistical Analysis Plan
SD	Standard Deviation
6MWD	6-minute walk distance
6MWT	6-minute walk test
SGRQ	St Georges Respiratory Questionnaire
SOC	System Organ Class
TEAE	Treatment Emergent Adverse Event
WLL	Whole Lung Lavage

2 Introduction

The statistical analysis plan (SAP) for the trial SAV006-03 is based on the final protocol version 5.0 24AUG2018.

The SAP describes in detail the analyses to be conducted and highlights any deviations from the analysis described in the protocol (see section 9). Deviations from methods described in this SAP, if any, will be specified in the clinical trial report.

The analysis is performed based on:

- The clinical database, which includes the electronic Case Report Forms (eCRF)

Reporting of the trial will be after the date of last subject last visit except for a safety update during the trial.

The trial is terminated early, and the final reporting will be done when all subjects have attended a final visit and the database is considered clean and locked.

3 Trial Characteristics

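### SAP 8.1.4 leaves respiration rate out of its list of vital signs, so no safety summary is planned for a variable the protocol requires

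*SAP*

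**What the plan says.** Protocol 10.8.3 lists the vital signs to be assessed at the flow-chart visits. Beside blood pressure, heart rate and oral temperature it includes "Resting respiration rate (breaths per minute), after 5 minutes sitting". Protocol 10.8 counts vital signs among the safety variables.

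SAP 8.1.4 has two sentences on the subject. The first gives the parameters: "Vital signs (heart rate, temperature, systolic and diastolic blood pressure) will be measured at each visit including an evaluation for each parameter". The second gives the analysis: "Continuous values of vital signs will be summarized by parameter and visit including change from baseline". The outputs are Table 14.3.2.1 (values) and Table 14.3.2.2 (change from baseline), both on the safety analysis set, and Listing 16.2.9.1 for all subjects. None of these titles names a parameter.

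SAP Section 2 undertakes to flag departures from the protocol's analysis in Section 9. Section 9 declares two: the added safety analysis set, and the unreported time off treatment.

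**The concern.** Safety is the primary objective, and protocol 4.3 states that "the potential dose-limiting toxicity of molgramostim would be based on pulmonary effects". Respiration rate is the only respiratory item among the protocol's vital signs, and it is the one the SAP does not name. A team that programs from the SAP alone would produce vital-sign tables without it, and the report would not say that a protocol-specified safety variable had been left out. SAP 8.2 calls for all Section 14.3 output in the safety update, so the same gap would carry over there. SAP 3.2 says the data will feed the continuing safety evaluation and possibly a future marketing application.

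**Working it through.** The plan gives no figure to reproduce. The check compares the two lists and then looks for respiration rate elsewhere in the SAP.

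**1. The lists side by side**

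| Measure | Protocol 10.8.3 | SAP 8.1.4 |
|---|---|---|
| Systolic blood pressure | yes | yes |
| Diastolic blood pressure | yes | yes |
| Heart rate | yes | yes |
| Respiration rate | yes | **no** |
| Temperature | yes | yes |

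Five measures become four: 5 − 4 = 1 missing, or 1/5 = 20% of the list.

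**2. Is it picked up elsewhere in the SAP?** No. It is not in Section 9, the change log, or the lists of tables, listings and figures. The SAP's list is closed, with no wording to suggest that its four items are examples.

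**3. Does the protocol exempt it from summary?** No. Protocol Section 11 applies summary statistics by visit to the trial data in general and makes no exception for vital signs.

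**4. What still reaches the report?**
- *Individual values.* Protocol Section 11 says that listings show everything recorded, so respiration rate belongs in Listing 16.2.9.1.
- *Investigator ratings.* Version 3.0 of the SAP removed the summary of vital-sign evaluations, so normal/abnormal ratings are not tabulated for any vital sign.
- *Adverse events.* Under protocol 10.9.2.5 an asymptomatic abnormal vital sign becomes an adverse event if it is clinically significant, meets a seriousness criterion or makes the subject discontinue. If there are symptoms, the symptom is reported. These events are tabulated on the safety analysis set.
- *Other respiratory measures.* SAP 7.2.1, 7.2.2 and 7.2.5 and the table list plan by-visit summaries, with change-from-baseline tables, for (A-a)DO₂, start and worst SpO₂, desaturation, FEV1, FVC and DLCO. Borg dyspnoea is also summarised. All use the full analysis set.

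**5. How far apart are the two analysis sets?** SAP 3.2 reports 60 enrolled, with 55 on treatment and 5 off treatment at termination. Taking that split as complete, at least 55 subjects were exposed, so the sets differ by at most 5/60 = 8.3%.

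**6. Upper bound on the affected data.** There are seven scheduled visits. With 55 to 60 subjects this gives at most 55 × 7 = 385 to 60 × 7 = 420 scheduled subject-visits. The true number is lower, because the trial closed early and not every subject reached Visit 7.

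**The case against.** The strongest reply is that the SAP excludes nothing. The four-item list sits in a sentence about measurement, the analysis sentence refers to vital signs in general, the table titles are generic, and the SAP states that it is based on protocol version 5.0. A programmer could properly include respiration rate. This stands to the extent that the finished tables cannot be known from the documents. It does not remove the point, because the four-item list is the only definition of vital signs that the SAP gives.

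A second reply is that respiratory safety is well covered. After the words quoted from protocol 4.3, the examples given are bronchoconstriction, cough, dyspnoea and loss of lung function. Respiration rate is not among them, and spirometry, DLCO and Borg dyspnoea are closer measures of these effects. This largely stands. Those summaries would show much of any gradual respiratory shift, and the two analysis sets barely differ. They are not a full substitute: the (A-a)DO₂ summary drops visits sampled on supplemental oxygen, and no respiratory measurement is planned for summary on the safety analysis set.

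A third reply is that Section 9 covers only departures from the analysis that the protocol describes, and the protocol describes none specific to vital signs. That is arguable, but the protocol's general rule on summaries does cover them.

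A reader might infer that respiration rate is lost, that it will never be reported, or that a gradual respiratory change would go unseen. The documents support none of these, given the listing rule, the generic table titles and the other respiratory summaries.

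**Conclusion.** The point holds in a limited form. The SAP does not name a safety variable that the protocol requires, plans no summary of it in the safety analysis set, and does not declare the omission. No primary or secondary endpoint is affected, and the individual values should still be listed. The size is one of five vital-sign measures, with 420 scheduled subject-visits as a ceiling. This is a minor inconsistency worth correcting because the correction is so cheap.

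Three assumptions apply. The eCRF, which is not among the documents, captured respiration rate as protocol 10.8.3 requires. The 55/5 split in SAP 3.2 accounts for all 60 enrolled subjects. Where the final IMPALA visit served as baseline, IMPALA recorded respiration rate; the documents do not say. If it did not, change from baseline would be missing for those subjects, but the by-visit values would be unaffected.

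**What to change.** Add respiration rate (breaths per minute) to the parameter list in SAP 8.1.4. Add it to Table 14.3.2.1 (value by visit) and Table 14.3.2.2 (change from baseline by visit). Confirm that Listing 16.2.9.1 shows it. If the sponsor prefers to leave it out, or the eCRF did not capture it, Section 9 should say so and give the reason.

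The cost is one added term in the SAP text and one extra block in each of two existing tables. There is no new collection, new output or change to any other analysis. If the SAP can no longer be revised, the summary can be added and identified in the clinical trial report as a departure from the SAP, a route that SAP Section 2 already provides.
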